² Patients entering the study currently active and established on CUTAQUIG in Study SCGAM-03 will have the Baseline Visit performed on the same day as Termination Visit on Study SCGAM-03. Procedures that are performed on the same day as part of Study SCGAM-03 Termination Visit that are also required as part of Study SCGAM-06 Baseline do not need to be repeated at the same visit.

³ Optional Onsite Visit. This visit is not required for patients who are infusing at their maximum volume.

⁴ Vital signs will be measured, and all laboratory samples will be collected, before IMP infusion (if applicable).

⁵ For females of child-bearing potential.

⁶ Increase volumes at each infusion site by up to a maximum increase of 25 mL/site for patients ≥ 40 kg or a maximum increase of 10 mL/site for patients < 40 kg every 4 weeks at each site visit. This increase can be achieved by reducing the total number of injection sites while keeping the same or lower flow rate parameters as received with their prior treatment. This cycle will continue until reaching a patient's maximum dose (in mL), maximum tolerated volume (maximum volume based on Investigator's decision of patient's tolerance) or 100 mL at 1 injection site –whichever is reached first. Further instructions are provided in Section 3.3.2 Dosing, Cohort 1.

⁷ Termination Visit MUST take place prior to the patient receiving any other IgG product.

Table 3: Cohort 2 (Increased Infusion Rate) – Flow Chart of Assessments

ASSESSMENTS	Treatment Period							Termination ⁷
	BL ^{1, 2}	4 ¹	8 ¹	12 ¹	16 ³	20 ³	24 ¹	
TREATMENT PERIOD VISIT WEEK OR TIMING								One week after last infusion
Body weight	X	X	X	X	X	X	X	
Physical examination	X			X			X	X
Vital signs ⁴	X	X	X	X	X	X	X	X
Urine pregnancy test ^{4, 5}				X			X	X
IgG trough levels ⁴	X	X	X	X	X	X	X	X
Hematology (CBC, WBC differential, hematocrit, hemoglobin) ⁴	X			X			X	X
Clinical Chemistry (sodium, potassium, glucose, ALT, AST, LDH, total bilirubin, blood urea nitrogen, creatinine) ⁴	X			X			X	X
Urine analysis: pH, glucose, ketones, leukocytes, hemoglobin ⁴	X			X			X	X
Serum retention samples: SCGAM-03 patients not participating in the Stabilization Period ⁴	X							
Serum retention samples: all patients ⁴								X
Hepatitis C samples: SCGAM-03 patients not participating in the Stabilization Period ⁴	X							
Hepatitis C samples: all patients ⁴								X
Infusion of IMP (on site) ⁶	X	X	X	X	X	X	X	
Check for local infusion site reactions	X	X	X	X	X	X	X	X
Patient diary hand-out and check	X	X	X	X	X	X	X	X
Quality-of-Life Questionnaire	X							X
Subject Questionnaire								X
Prior/Concomitant medication	Throughout the study							
Adverse events	Throughout the study							

Required Onsite Visit for all patients.

² Patients entering the study currently active and established on CUTAQUIG in Study SCGAM-03 will have the Baseline Visit performed on the same day as Termination Visit on Study SCGAM-03. Procedures that are performed on the same day as part of Study SCGAM-03 Termination Visit that are also required as part of Study SCGAM-06 Baseline do not need to be repeated at the same visit.

³ Optional Onsite Visit. This visit is not required for patients who are infusing at their maximum rate.

⁴ Vital signs will be measured, and all laboratory samples collected, before IMP infusion (if applicable).

⁵ For females of child-bearing potential.

⁶ Increase flow rates by up to 25 mL/hr/site for patients \geq 40 kg or 10 mL/hr/site for patients $<$ 40 kg every 4 weeks at each site visit until reaching either 1: a maximum flow rate (100 mL/hr/site) or the maximum rate achievable by the pump, or 2) the maximum tolerated flow rate (based on Investigator's decision of patient's tolerance) – whichever is reached first.

⁷ Termination Visit MUST take place prior to the patient receiving any other IgG product.

Table 4: Cohort 3 (Every Other Week Dosing) – Flow Chart of Assessments

ASSESSMENTS		Treatment Period			Termination
TREATMENT PERIOD VISIT WEEK OR TIMING	BL ^{1, 2}	4 ¹	12 ¹	24 ¹	Two weeks after last infusion ⁶
Body weight	X	X	X	X	
Physical examination	X		X	X	X
Vital signs ³	X	X	X	X	X
Urine pregnancy test ^{3, 4}			X	X	X
IgG trough levels ³	X	X	X	X	X
Hematology (CBC, WBC differential, hematocrit, hemoglobin) ³	X		X	X	X
Clinical Chemistry (sodium, potassium, glucose, ALT, AST, LDH, total bilirubin, blood urea nitrogen, creatinine) ³	X		X	X	X
Urine analysis: pH, glucose, ketones, leukocytes, hemoglobin ³	X		X	X	X
Serum retention samples: SCGAM-03 patients not participating in the Stabilization Period ³	X				
Serum retention samples: all patients ³					X
Hepatitis C samples: SCGAM-03 patients not participating in the Stabilization Period ³	X				
Hepatitis C samples: all patients ³					X
Infusion of IMP (on site) ⁵	X	X	X	X	
Check for local infusion-site reactions	X	X	X	X	X
Patient diary hand-out and check	X	X	X	X	X
Quality-of-Life Questionnaire	X				X
Subject Questionnaire					X
Prior/Concomitant medication		Throughout the study			
Adverse events		Throughout the study			

¹ Required Onsite Visit for all patients.² Patients entering the study currently active and established on CUTAQUIG in Study SCGAM-03 will have the Baseline Visit performed on the same day as Termination Visit on Study SCGAM-03. Procedures that are performed on the same day as part of Study SCGAM-03 Termination Visit that are also required as part of Study SCGAM-06 Baseline do not need to be repeated at the same visit.³ Vital signs will be measured, and all laboratory samples collected, before IMP infusion (if applicable).⁴ For females of child-bearing potential.⁵ Patients entering this cohort must already be established on weekly dosing for a minimum of 12 weeks prior to Screening. Patients will receive double the mg/kg weekly dose and begin an every other week dosing schedule. Infusion flow rates will be determined by the patient and Investigator, but initially should not exceed the patient's prior infusion rate. When switching from weekly to every other week dosing, infusion volumes increases per site must not exceed 25 mL for patients \geq 40 kg or a maximum increase of 10 mL/site for patients $<$ 40 kg at the Treatment Period Baseline Visit. If a patient's doubling of their weekly dose requires dosing with a volume of more than the maximum allowed volume increase per injection site (25 mL/site or 10 mL/site, dependent on patient body weight), they will be required to increase the number of infusion sites to remain below the maximum body-weight dependent volume increase. If this occurs, after 2 infusions the patient may remove 1 of the newly introduced injection sites as long as the volume per injection site increase limit is not exceeded.⁶ Termination Visit MUST take place prior to the patient receiving any other IgG product.

PROTOCOL SIGNATURES

This study is intended to be conducted in compliance with the protocol,
Good Clinical Practice and applicable regulatory requirements.

[REDACTED] Signature

[REDACTED] Date

Octapharma Pharmazeutika Produktionsgesellschaft mbH
[name]
[contact]

11.09.2019

[REDACTED] Signature

[REDACTED] Date

Octapharma USA, Inc.
[name]
[name]
[contact]

10 SEP 19

[REDACTED] Signature

[REDACTED] Date

Octapharma Pharmazeutika Produktionsgesellschaft mbH
[name]
[contact]

11-SEP-2019

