Tertiary Objective:

A tertiary objective of this study is to evaluate patient satisfaction of various study parameters (such as switching to CUTAQUIG from another SCIG product, satisfaction with infusion pump, changes in infusion regimen parameters, general infection/general observations) using a study-specific questionnaire.

Study Design:

The study is a prospective, open-label, non-controlled, 3-arm, multicenter, phase 3 study.

Patients with a history of primary immunodeficiency (PI) disease that are currently on a stable dose of subcutaneously administered immunoglobulin (SCIG) treatment may be enrolled.

Stabilization Period

After completing the Screening Period and being assigned to 1 of 3 cohorts (as described below), patients will enter a 4-week Stabilization Period. During this period, patients will receive their first 4 CUTAQUIG infusions (Stabilization Period Weeks 0, 1, 2, and 3) at the same body-weight dependent dose (mg/kg) and infusion flow rate (mL/hr/site) as their previous SCIG product; however, this flow rate should not exceed maximum infusion rates listed in protocol.

Note: patients entering the study for participation in Cohort 3 must already be established on a weekly infusion schedule for a minimum of 12 weeks prior to the Screening Visit.

Patients entering the study already established on every other week dosing must enter either Cohort 1 or Cohort 2 and will be required to dose weekly beginning at the Stabilization Week 0.

Note: patients entering the study currently active and established on CUTAQUIG in Study SCGAM-03 will have already been stabilized on CUTAQUIG and would go directly into the Treatment Period following the Screening Visit. The Screening Visit of Study SCGAM-06 will occur on the same day as the final dosing visit for Study SCGAM-03. Procedures performed for Study SCGAM-03 that are also required for the Study SCGAM-06 Screening Visit do not need to be repeated at the same visit. Patients that completed the SCGAM-03 study and went on a commercial SCIG

Name of Sponsor/Company: Octapharma USA, [name]	
Name of Investigational Product: CUTAQUIG	Protocol Identification Code: SCGAM-06
Name of Active Ingredient: Human Normal Immunoglobulin	Date of Final Protocol: 28-Aug-2019

product prior to screening for SCGAM-06 are required to enter the Stabilization Period.

Treatment Period

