
Test Product, Dose, and Mode of Administration:
 
CUTAQUIG, human normal immunoglobulin for subcutaneous (SC) administration.
 
CUTAQUIG will be administered by SC infusion every week (± 2 days, Cohort 1 and Cohort 2), every other week (± 2 days, Cohort 3) at the doubled weekly dose. The dosing frequency will be determined by cohort assignment.
 
Patients will receive the same mg/kg body weight dose as their previous SCIG product prior to study entry.
 
If, during the study, a patient's body weight changes by $>5\%$ from the first infusion of IMP, the dose will be adjusted to keep a constant mg/kg body weight basis. Additional adjustments will be made by the Investigator at study visits if the patient's body weight changes $>5\%$ from the previous adjusted weight.
 
Each patient's CUTAQUIG dose may be individualized, if considered necessary by the Investigator, by titrating upward or downward.
 
Batch (lot) numbers will be reported in the final report of the study.

Duration of Treatment:
 
Individual patient participation will be approximately 30 to 32 weeks:
 
• Screening Period: 1 to 2 weeks*• Stabilization Period: 4 weeks**• CUTAQUIG Treatment Period: 24 weeks (6 months)• Termination Visit: 1 week after last CUTAQUIG infusion for Cohort 1 and Cohort 2; 2-weeks after last CUTAQUIG infusion for Cohort 3

Name of Sponsor/Company: Octapharma USA, [name]	
Name of Investigational Product: CUTAQUIG	Protocol Identification Code: SCGAM-06
Name of Active Ingredient: Human Normal Immunoglobulin	Date of Final Protocol: 28-Aug-2019

* Patients entering the study established on weekly SCIG infusions will have a 1-week (± 2 days) Screening Period. Patients entering the study established on every other week dosing will have a 2-week (± 2 days) Screening Period.

** Patients entering the study currently active and established on CUTAQUIG in Study SCGAM-03 will skip Stabilization Period.

Reference Therapy, Dose, Mode of Administration:

Not applicable.

Study Outcome Parameters (Primary and Secondary Endpoints):**Primary Endpoint Parameters:**

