The co-primary objectives are to compare total IgG trough levels from weekly infusions to every other week infusions, to assess safety and tolerability of CUTAQUIG being administered according to 3 different infusion parameters, and to assess efficacy parameters when switching from weekly infusions to every other week infusions. These will be assessed using the following safety variables:

- Change in individual total IgG trough levels from weekly infusions to every other week infusions
- Occurrence of treatment-emergent AEs (TEAEs) throughout the entire Stabilization and Treatment Periods starting with the first infusion of investigational medicinal product (IMP)
- Occurrence of TEAEs temporally associated with CUTAQUIG delivered during the Treatment Period
- Occurrence of TEAEs temporally associated with CUTAQUIG delivered during the Stabilization Period
- TEAEs by speed of infusion
- Local infusion-site reactions
- Laboratory parameters (hematology, clinical chemistry, and basic urinalysis)

Secondary Endpoint Parameters:

Secondary objectives will evaluate quality of life, along with additional evaluations of CUTAQUIG safety and efficacy being administered according to 3 different infusion parameters. These will be assessed using the following variables:

Name of Sponsor/Company: Octapharma USA, [name]	
Name of Investigational Product: CUTAQUIG	Protocol Identification Code: SCGAM-06
Name of Active Ingredient: Human Normal Immunoglobulin	Date of Final Protocol: 28-Aug-2019

- Quality of Life questionnaires
- Measurement of individual profiles of IgG trough levels over time (all cohorts)
- Monitoring for all infectious disease occurrence, resolution, and antibiotic use
- Occurrence of serious bacterial infections (SBIs)
- Vital signs (blood pressure, pulse, body temperature, respiratory rate)

Tertiary Endpoint Parameters:

The tertiary objective will evaluate patient satisfaction of the study parameters (such as switching to CUTAQUIG from another SCIG product, satisfaction with infusion pump, changes in infusion regimen parameters, general infection/general observations). This will be assessed using the following parameter:

- Subject Questionnaire

Study Procedures:

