After completing the Screening Period during which they will be assigned to 1 of the 3 study cohorts, patients will enter a 4-week Stabilization Period. During the Stabilization Period, patients will receive CUTAQUIG infusions at the same body-weight dependent dose and infusion rate as their previous SCIG product prior to entering the Treatment Period; however, this flow rate should not exceed maximum infusion rates listed in protocol (Section 5.5.3). Patients will receive 4 CUTAQUIG infusions during the Stabilization Period. Patients entering the study currently active and established on CUTAQUIG in Study SCGAM-03 will have already been stabilized on CUTAQUIG and will go directly into the Treatment Period following the Screening Visit. Patients that completed the SCGAM-03 study and went on a commercial SCIG product prior to entering SCGAM-06 are required to enter the Stabilization Period. During the Treatment Period, patients will receive CUTAQUIG infusions according to their assigned-cohort infusion parameters.

Throughout the study, the following interventions and procedures will be performed at predefined time points (Section 6.1.2 and the Flow Charts of Assessments Table 1 [Screening and Stabilization Periods], Table 2 [Cohort 1], and Table 3 [Cohort 2], Table 4 [Cohort 3]): blood draws for laboratory assessments, body weight measurement, patient diary review, physical examination including vital signs, local infusion-site reaction assessments, urine sampling, urine pregnancy tests, QoL assessments, and the Subject Questionnaire. AEs and any changes in concomitant medications will be recorded throughout the study period.

Patients who enter and participate in one cohort may not enter another cohort at a later time.

An Independent Data Monitoring Committee (IDMC) will periodically review relevant data throughout the study with emphasis on adverse events including serious adverse events and thromboembolic events.

The study will be conducted at study sites in the USA.

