9.1 Determination of Sample Size

Approximately 65 patients who meet eligibility criteria will be enrolled in the study:

- At least 15 patients in Cohort 1
- At least 15 patients in Cohort 2
- At least 35 patients in Cohort 3

The co-primary endpoints will be analyzed descriptively, and no formal sample size calculation was done for the overall number of patients enrolled.

For Cohort 3 we plan for a confirmative analysis to evaluate whether the total IgG trough levels are maintained by an every other week dosing regimen; the following pair of hypotheses will be tested:

$$H_a: T_{eow} > T_w - 1 \quad \text{vs.} \quad H_0: T_{eow} \leq T_w - 1$$

where T_{eow} is the mean total IgG trough on steady-state dosing every other week, T_w is the same for weekly dosing, and a maximum decrease of 1 g/L for the mean total IgG trough level is considered acceptable.

T_w will be determined after completion of the Stabilization Period, T_{eow} at the final study visit.

This one-sided hypothesis will be tested by a paired t-test at the alpha=2.5% level of significance. Assuming 3.0 for the standard deviation common to both members of a pair, and 0.8 as the correlation between members of a pair, this results in a required minimum of 31 evaluable patients to achieve a power of 80%.

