7. General Issues for Statistical Analysis

Descriptive summaries will be presented for each of the primary and secondary variables. In general, summaries will be completed for all patients overall and by study cohort if applicable.

Continuous, quantitative variable summaries will in general include the number of patients with non-missing values (N), mean, standard deviation, median, minimum and maximum, 1st and 3rd quartile.

Categorical, qualitative variable summaries will include the frequency and percentage of patients who are in the particular category. In general the denominator for the percentage calculation will be based upon the total number of patients in the analysis population unless otherwise specified.

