8.1. Disposition of Subjects and Withdrawals

All patients enrolled in the study will be accounted for. Descriptive summaries of population data will be provided overall and by study cohort; these will include

- The frequency and percent of patients in each analysis population, age strata (pediatric and adult) and enrollment group
- The disposition of patients (including number of patients enrolled, number of patients treated, number of completers)
- study withdrawals by reason of withdrawal

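### Direct SCGAM-03 entrants appear in the Treatment Period but not in Stabilization, and no listed safety table separates them, so the two co-primary TEAE summaries describe different patients

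*Protocol*

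**What the plan says.** The protocol has two routes into the Treatment Period.

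- **Through Stabilization.** In this period "patients will receive their first 4 CUTAQUIG infusions" at their previous dose and flow rate (Protocol, Study Outline). Some former SCGAM-03 patients take this route: "Patients that completed the SCGAM-03 study and went on a commercial SCIG product prior to entering SCGAM-06 are required to enter the Stabilization Period" (Protocol 3.2).
- **Directly.** Patients still active on CUTAQUIG in SCGAM-03 "will have already been stabilized on CUTAQUIG and would go directly into the Treatment Period" after Screening (Protocol, Study Outline; also 3.2 and 6.1.2).

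Protocol 9.1 sets minimum cohort sizes of 15, 15 and 35 (for example "At least 15 patients in Cohort 1"). Neither document states or caps the number of direct entrants.

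The co-primary variables include "Occurrence of TEAEs temporally associated with CUTAQUIG delivered during the Stabilization Period" and the matching variable for the Treatment Period (Protocol 3.1.1; SAP 3.2.1). SAP 10.1 tabulates both as patient incidence by system organ class and preferred term. On grouping, SAP section 7 says that "summaries will be completed for all patients overall and by study cohort if applicable". It also makes the whole analysis population the default percentage denominator, and SAP 10.1 does not override this for the Stabilization table. The one place that might separate entry routes is the disposition summary in SAP 8.1, by "age strata (pediatric and adult) and enrollment group"; the last term is not defined. The per-infusion ratio in SAP 7.4 and 10.2 is calculated per patient over all infusions, with no split by period or entry route.

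**The concern.** The study has no control group and no randomization. Stabilization infusions use the previous dose and flow rate, and Treatment infusions use the modified regimen. A reader who asks whether a modified regimen changed tolerability will naturally set one period's summary beside the other's. Those summaries do not cover the same people, because direct entrants contribute only to the second.

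If their reaction rate differs from that of the patients who went through Stabilization, part of any difference between periods reflects who was observed and not what the regimen did. The default denominator adds a second distortion, since direct entrants enter the Stabilization percentage as patients without an event although they had no infusion there. At stake is the interpretation of two co-primary safety variables within each cohort.

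**Working it through.** The plan gives no figure on this point. Its only sample-size figure, 31 evaluable patients for the Cohort 3 IgG test, reproduces (power 0.810 at 31, 0.797 at 30) and is not affected.

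**Inputs from the documents**
- Stabilization: 4 weekly infusions for patients who enter it, none for direct entrants.
- Treatment: Baseline to Week 24 inclusive gives about 25 weekly infusions (Cohorts 1 and 2) or 13 every other week (Cohort 3).
- Local reactions per infusion across published SCIG studies: 0.028 to 0.697 (Protocol 1.1). This is spread between studies, not a contrast between entry routes.

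**Assumptions, because the documents give none of these**
- f: share of Treatment infusions from direct entrants. With equal follow-up this is also their share of patients.
- q: their reaction rate relative to stabilized patients.
- RR: the true within-patient ratio, Treatment to Stabilization.
- p: the per-infusion probability in Stabilization. Infusions are taken as independent.

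**1. Per-infusion scale**

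Pooled ratio = RR × [(1 − f) + f × q]. With RR = 1.5 and q = 0.5:
- f = 0.20: 1.5 × 0.90 = 1.35
- f = 0.33: 1.5 × 0.833 = 1.25
- f = 0.50: 1.5 × 0.75 = 1.125

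A true rise disappears (ratio ≤ 1) only if f ≥ (1 − 1/RR)/(1 − q):

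| RR | q = 0.25 | q = 0.5 | q = 0.75 |
|---|---|---|---|
| 1.25 | 27% | 40% | 80% |
| 1.5 | 44% | 67% | impossible |
| 2.0 | 67% | 100% | impossible |

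At q = 1 there is no attenuation. If the comparison is restricted to patients treated in both periods, f = 0 and the ratio equals RR whatever q is.

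**2. Patient-incidence scale, which the planned tables use**

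Incidence over k infusions = 1 − (1 − p)^k.
- Exposure alone, p = 0.028 and no true rise: 10.7% over 4 infusions, against 50.8% over 25 or 30.9% over 13.
- With p = 0.10, RR = 1.5, q = 0.25, f = 0.33 and 25 infusions: Stabilization is 34.4% on its own denominator and 22.9% on the default one (two thirds of 34.4%). Treatment is 86.0%.
- A case built to favour masking: 10 of 15 patients are direct entrants, rates are 0.30 (stabilized) and 0.15 (direct), no regimen effect. Stabilization is 1 − 0.70^4 = 76.0% on its own denominator, or 5/15 × 76.0% = 25.3% on the default. Treatment is [5 × (1 − 0.70^25) + 10 × (1 − 0.85^25)]/15 = (5 × 0.9999 + 10 × 0.9828)/15 = 98.8%.

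On the default denominator, expected Stabilization incidence is (1 − f) × [1 − (1 − p)^4]. For RR ≥ 1 and full follow-up, the stabilized patients alone contribute at least that much to Treatment. Treatment incidence therefore cannot fall below Stabilization incidence in expectation.

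The two scales push in opposite directions. The same mix also enters the flow-rate tables in SAP 10.1, where the Stabilization infusions come only from patients who were stabilized.

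**The case against.** The strongest objection is to a reading that this design invites: that direct entrants are selected for tolerating CUTAQUIG, so pooling them hides a true rise and makes the modified regimens look neutral or better. The documents do not support that reading.

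- **Direction.** The planned period tables are patient incidences over 4 against 13 to 25 infusions. Even the masking-friendly case above shows an apparent rise, about 25% to 99%.
- **Scale.** No per-infusion rate by period is planned, so attenuation arises only if someone divides event counts by infusions.
- **Selection.** The protocol calls these patients stabilized and established, not selected for tolerance. That they tolerate CUTAQUIG is a reasonable inference. But every entrant has at least 3 months on a stable SCIG dose, and persistent reactions to plasma products and routine premedication are exclusions.
- **Comparator.** No Stabilization-versus-Treatment contrast or test is planned. Protocol 9.2 says only that presentation by cohort is meant to help comparison between regimens.
- **Experience.** Stabilization also holds former SCGAM-03 patients who had moved to a commercial product, so it is not purely a CUTAQUIG-naïve group.

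All of this stands against the stronger reading. It does not remove the structural point: the two co-primary summaries cover different patients, and the default denominator misstates who was at risk in Stabilization. By-patient AE listings and the separate table list (SAP 2 and 13) could help, but the SAP commits to no summary that separates the routes.

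**Conclusion.** The point holds as confounding of unknown direction. It does not hold as a demonstrated masking of harm. Direct entrants contribute to one of two paired co-primary summaries only, nothing listed separates them, and as written they dilute the Stabilization percentage.

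The size depends on f and q, which the documents do not give. On a per-infusion scale, with an assumed RR of 1.5 and q of 0.5, the ratio is attenuated to between 1.35 and about 1.12 for shares of 20% to 50%. Full masking of that rise needs 67% direct entrants. With no direct entrants the mix effect is zero. In the planned incidence tables the denominator and exposure length exaggerate a rise instead.

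The safety presentation should be corrected before analysis. The Cohort 3 sample size is not affected.

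**What to change.** - **SAP 10.1, denominator.** Use only patients who infused in Stabilization as the denominator for that period.
- **SAP 10.1, added presentation.** Within each cohort, show temporally associated TEAEs and local site reactions by period, per infusion started, for patients who infused in both periods. Put direct SCGAM-03 entrants in a separate Treatment Period column and keep the all-patient column as the total.
- **SAP 8.1.** Define enrollment group as entry route: direct from SCGAM-03, or through Stabilization. SCGAM-03 completers who moved to a commercial SCIG belong with the stabilized patients.
- **Definitions to reconcile.** SAP 7.4 defines the stabilization period only for patients who did not take part in SCGAM-03, whereas Protocol 3.2 sends some of them through it. Protocol 7.3.1.1 ties treatment-emergence to the Stabilization Week 0 infusion, which direct entrants never receive; Protocol 9.2.3.1 and SAP 10.1 use the first CUTAQUIG infusion.

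No new data are needed: the cost is a few SAP sentences and extra columns. Cells will be small in the 15-patient cohorts. The per-infusion scale deals with exposure length and the both-period restriction deals with patient mix. Neither removes habituation over time, so the comparison remains descriptive.
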